7.1.3. Pooling Algorithm for Analysis Centers

Data will be pooled across the different centers.

7.1.4. Visit Windows

Refer to CTP section 8. Visit windows will be taken into account for the analysis of immunogenicity results, see section [7.7.1](#).

7.1.5. Analyses by Cohort and Pooled Across Cohorts

All analyses are planned to be performed within each cohort separately, unless explicitly indicated that data will be pooled across cohorts.

7.2. Participant Dispositions

Participant information will be shown for the full analysis set.

The number of participants in the following disposition categories will be summarized throughout the study by vaccine regimen and overall:

- participants screened
- participants in the FAS
- participants vaccinated and not randomized
- participants randomized and not vaccinated
- participants in the PPI
- participants in the PPE
- participants who discontinued study
- participants who discontinued vaccination
- reasons for termination

Also, the number of participants and percentage per phase will be tabulated.

7.2.1. Demographics and Baseline Characteristics

The following demographic and baseline characteristics will be summarized.

[Table 4](#) presents a list of the demographic and baseline variables that will be summarized by vaccine regimen and overall for the FAS.

Table 4: Demographic Variables

Continuous Variables:	Summary Type
Age (years)	Descriptive statistics (N, mean, standard deviation [SD], median and range [minimum and maximum]).
Weight (kg)	
Height (cm)	
Body Mass Index (BMI) (kg/m ²)	
Categorical Variables	
Sex (male, female, undifferentiated)	
Race ^a (American Indian or Alaska Native, Asian, Black or African American, Native Hawaiian or other Pacific Islander, White, Multiple)	
Ethnicity (Hispanic or Latino, not Hispanic or Latino)	
Study center	
SARS-CoV-2 Seropositivity status at screening	

^aIf multiple race categories are indicated, the Race is recorded as 'Multiple'

7.2.2. Protocol Deviations

Major protocol deviations will be summarized. Major protocol deviations which have a potential impact on immunogenicity will be flagged in the listings.

7.2.3. Concomitant Medications

The analysis of concomitant therapies will be done using the WHO drug coded terms.

Based on their start and stop date, concomitant therapies will be reported in each applicable phase.

If a concomitant therapy record misses components of its start and/or stop dates (time, day and/or month and/or year):

- In case of partial start or stop dates, the concomitant therapy records will be allocated to periods using the available partial information, without imputations. If, for example, only month and year are available, these will be compared to the month and the year of the periods, and the concomitant therapy record will be allocated to the period(s) where these date parts match. This rule may lead to assignment to multiple periods.
- In case of a completely missing start date, the concomitant therapy will be considered as having started before the trial.
- In case of a completely missing end date, the concomitant therapy will be considered as ongoing at the end of the trial.

There will be special attention to any systemic use of analgesics/antipyretics, started during 8 days following each vaccination (00:00 of day of vaccination + 7 days). Following CMCLASCD (ATC/DD codes) will be used for this: N02A (OPIOIDS) and N02B (OTHER ANALGESICS AND ANTIPYRETICS), M01A (ANTIINFLAMMATORY AND ANTIRHEUMATIC PRODUCTS, NON-STEROIDS) and M01B (ANTIINFLAMMATORY/ANTIRHEUMATIC AGENTS IN COMBINATION). The classes will be added in a footnote in all related tables and listings. For the use of analgesics/antipyretics which are taken on the day of vaccination an exception is made in case the time is before vaccination. In this case the concomitant medication is also allocated to the post-dose period.

Participants with COVID-19-like signs and symptoms will collect concomitant medications since symptom onset. These will be tabulated and listed; they will also be included in the programmed patient narratives.

7.3. Primary Endpoint(s) Analysis

The primary endpoints in this study, are:

All participants in Cohorts 1, 2, and 3:

- Solicited local and systemic adverse events (AEs) for 7 days after each vaccination in the primary regimen
- Unsolicited AEs for 28 days after each vaccination in the primary regimen
- For the primary endpoint: Serious adverse events (SAEs) from the first vaccination until 1 year after the second vaccination for Cohorts 1 and 3, and until 6 months after the primary regimen for Cohort 2

7.3.1. Definition of Endpoint(s)

Solicited AEs are used to assess the reactogenicity of the study vaccine and are predefined local (at the injection site) and systemic events for which the participant is specifically questioned and which are noted by participants in their diary. Unsolicited AEs are all AEs for which the participant is not specifically questioned.

7.3.2. Estimand

Not applicable

7.3.3. Analysis Methods

Refer to section [7.6](#).

7.4. Secondary Endpoint(s) Analysis

7.4.1. Key/Confirmatory Secondary Endpoint(s)

The secondary endpoints in this study, are:

Humoral Immune Response

All participants in Cohorts 1, 2, and 3:

- SARS-CoV-2 neutralization: SARS-CoV-2 neutralizing titers in serum measured by a virus neutralization assay (VNA [wild-type virus and/or pseudovirion expressing S protein])
- SARS-CoV-2-binding antibodies measured by enzyme-linked immunosorbent assay (ELISA): Analysis of antibodies binding to the SARS-CoV-2 S protein.

Cellular Immune Response

A subset of participants in Cohorts 1, 2, and 3:

- Th1 and Th2 immune responses as assessed by flow cytometry after SARS-CoV-2 S protein peptide stimulation of peripheral blood mononuclear cells (PBMCs) and intracellular staining [ICS] including CD4+/CD8+, IFN γ , interleukin [IL] 2, TNF α , IL-4, IL-5, IL-13, and/or other Th1/Th2 markers.

7.4.1.1. Definition of Endpoint(s)

Refer to section [7.7.1](#).

7.4.1.2. Estimand(s)

Not Applicable

7.4.1.3. Analysis Methods

Refer to section [7.7.1](#).

7.5. Tertiary/Exploratory Endpoint(s) Analysis

The exploratory endpoints in this study, are:

Safety and Reactogenicity:

All participants in Cohort 2:

- Solicited local and systemic AEs for 7 days after each booster vaccination time point
- Unsolicited AEs for 28 days after each booster vaccination time point
- SAEs from the first booster vaccination time point until the end of the study

Humoral Immune Response:

Exploratory analyses may include the following assays for a subset of participants in Cohorts 1 and 3:

- SARS-CoV-2 neutralization as assessed by alternative SARS-CoV-2 neutralization assays (different from the VNA used for the secondary endpoint).
- Adenovirus neutralization.
- Functional and molecular antibody characterization (eg, avidity, Fc receptor interaction, antibody isotyping).
- Epitope-specificity characterization for B- and T-cells.
- Cytokine profiling: Analysis of cytokines, chemokines, and other proteins of the innate or adaptive immune response in the serum or plasma.
- Passive transfer: Analysis of immune mediators correlating with protection against experimental SARS-CoV-2 challenge in a suitable animal model.

Cellular Immune Response:

Exploratory analyses may include the following assays for a subset of participants in Cohorts 1, 2, and 3:

- Single IFN γ and IL-4 enzyme-linked immunospot (ELISpot) assay after stimulation of PBMCs with SARS-CoV-2 S protein peptides.
- Analysis of gene expression in cells stimulated with SARS-CoV-2 S protein peptides, or in unstimulated cells (ex vivo).
- Cytokine profiling: Analysis of cytokines, chemokines, and other proteins of the innate or adaptive immune response in cells stimulated with SARS-CoV-2 S protein peptides, or in unstimulated cells (ex vivo).

A subset of participants in Cohort 2 only:

- Analysis of the phenotype of antigen-specific T and B cells, assessed by single cell analysis (on frozen or Smart tube-isolated PBMCs).

In addition to these immunogenicity-related exploratory endpoints, the following efficacy-related exploratory endpoints are defined in this study:

- The number of molecularly confirmed COVID-19 cases in Ad26.COV2.S versus placebo recipients in the overall study
- The number of participants with positive non-S protein ELISA (eg, N ELISA), if such an assay can be developed, in the Ad26.COV2.S and placebo groups
- Presence and severity signs and symptoms of COVID-19
- Confirmation of SARS-CoV-2 infection by molecular testing

The following endpoints are defined to examine the immune response in vaccinated individuals after natural infection and to explore other potentially informative biomarkers (eg, those associated with more severe disease):

- Confirmation of SARS-CoV-2 infection by molecular testing
- SARS-CoV-2 neutralizing titers in serum measured by a VNA (wild-type virus and/or pseudovirion expressing S protein)
- SARS-CoV-2-binding antibodies measured by ELISA: Analysis of antibodies binding to the SARS-CoV-2 S protein
- Functional and molecular antibody characterization
- Analysis of gene expression by RNA transcript profiling

7.6. (Other) Safety Analyses

Safety analyses will be performed on the FAS. Continuous variables will be summarized using the following statistics, as appropriate: number of observations, arithmetic mean (mean), standard deviation (SD), standard error (SE), median, quartiles (Q1 and Q3), minimum and maximum. Frequencies and percentages (one decimal place) will be generated for categorical variables. No formal comparisons between groups will be provided.

Safety data will be analyzed by study intervention regimens as designed per protocol^a. In addition, safety data will be analyzed by intervention regimens as designed per protocol and participant seropositivity status at screening. Data will be presented by period (post Dose 1, post Dose 2, post Booster 1, and post Booster 2, as applicable) as well as over the entire regimen, and for Cohorts 2a and 2b over the entire primary regimen and over the entire booster regimen. Denominator for the percentages is the number of participants in the considered population and phase for a certain regimen (incidence per 100 participants/phase).

Exploratory analyses by age (e.g. 18-40 years and 41-55 years) may be performed in Cohort 2.

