7.6.3. Analysis of Adverse Events

Number and percentage of participants with at least one particular AE (unsolicited/solicited) will be tabulated. Unsolicited AEs will be summarized by System Organ Class and Preferred Term. Solicited AEs will be summarized by class (administration site/systemic) and Preferred Term.

For solicited AEs following tables will be provided: summary, by worst severity grade, at least grade 3, related (systemic only), time to onset (in days) and duration (in days) for most frequent events and body temperature. Note: Duration is defined as number of days from the start of the event until resolution of the event. The time to first onset is defined as (date of first onset – reference date + 1). The reference date is the start date of the vaccination period.

^a As indicated previously, all analyses, including the safety analyses, will be conducted by actually received vaccine (“as treated” principle). The sentence “by study intervention regimens as designed per protocol” indicates that the statistical tables are designed with the planned vaccine regimens as columns. Therefore, participants who receive e.g. “Placebo, Placebo” instead of “Ad26.COV2.S 5x10¹⁰ vp, Placebo” will appear in the “Placebo, Placebo” column. However, to avoid sparse columns, participants who receive e.g. “Placebo, Ad26.COV2.S 5x10¹⁰ vp” (which is not a planned vaccine regimen) will be excluded from the statistical tables. They will be included in the listings, as well as in the programmed patient narratives where they will appear as “Subjects with vaccine misallocation”.

For unsolicited AEs, the following tables will be provided: summary table (including SAE, fatal outcome, and discontinuation), all events, most frequent, at least grade 3, permanent stop of vaccine, related, and SAE.

As a general remark, COVID-19 cases will be analyzed separately (see section [7.7.3](#)).

- SAEs that are COVID-19 related will not be included in the SAE tables, but will be included and flagged in the SAE listings. In MedDRA version 23.0, Preferred Terms (PT codes) “COVID-19 (10084268)”, “COVID-19 pneumonia (10084380)”, “Suspected COVID-19” (10084451), “Asymptomatic COVID-19 (10084459)”, “Coronavirus infection” (10051905), “Severe acute respiratory syndrome” (10061982), “SARS-CoV-2 carrier” (10084461), “Exposure to SARS-CoV-2” (10084456), and “Occupational exposure to SARS-CoV-2” (10084394) will be considered COVID-19 related AEs^a.

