7.7. Other Analyses

7.7.1. Immunogenicity Analyses

The analysis of immunogenicity will use the PPI set. Immunogenicity analyses will also be done on the FAS (participants who became infected during the study will be analyzed as a subgroup and shown in the graphs using different colors and symbols). Data will be analyzed by vaccine regimen, and by vaccine regimen and participant seropositivity status at screening^a. Data will be presented by scheduled time point. For the PPI analysis, samples taken outside of the allowed window will be excluded from the tables and graphs (but will be included in the listings and clearly marked as results not included in the PPI analyses). For the FAS analysis, samples taken outside of the allowed window will be included.

Note: analyses that are potentially unblinding at the individual participant level (e.g. graphs showing individual data tied to COVID-19 infection status, especially when the number of COVID-19 infections is low and/or when time of infection is indicated) will be carried out after official unblinding of the trial, or will be carried out exclusively on specific cohorts (or other clearly defined subgroups) after these are unblinded. Alternatively, prior to unblinding, these analyses can be performed in a completely blinded manner (e.g. tables with only a single column pooling all regimens).

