7.7.1.7. Statistical Modeling of the Immune Responses

Statistical modeling will be undertaken to assess the influence of demographic variables and baseline characteristics on selected immune responses. These analyses will be performed on the PPI analysis set, excluding participants in the regimens that received no active vaccine. The following are pre-planned statistical analyses:

- Linear regression analysis of 28 days post Dose 1, pre-Dose 2 and of 28 days post Dose 2 psVNA titers on demographic and baseline characteristics and control variables, using pooled data from all regimens and all cohorts.
- One model for 28 days post Dose 1, one for pre-Dose 2 and one for 28 days post Dose 2
- psVNA titers enter the model on the \log_{10} scale.

- Demographic variables: age (continuous), BMI (continuous), sex (categorical: male vs. female), race (categorical: Black or African American vs. White vs. Other).
- Baseline characteristics: baseline SARS-CoV-2 seropositivity status (categorical: Positive vs. Negative) and baseline VNA titers against the Ad26 vector (continuous, on the \log_{10} scale).
- Control variables: single-dose vs. two-dose regimen and high-dose vs. low dose regimen.
- Linear regression analysis of 28 days post Dose 1, pre-Dose 2 and of 28 days post Dose 2 wild type VNA titers on demographic and baseline characteristics and control variables, using pooled data from all regimens and all cohorts. Same considerations as for psVNA titers.
- Linear regression analysis of 28 days post Dose 1, pre-Dose 2 and of 28 days post Dose 2 ELISA antibody concentrations on demographic and baseline characteristics and control variables, using pooled data from all regimens and all cohorts. Same considerations as for psVNA titers.
- Penalized logistic regression analysis (using Firth's method) of 28 days post Dose 1, pre-Dose 2 and of 28 days post Dose 2 responder status for psVNA on demographic and baseline characteristics and control variables, using pooled data from all regimens and all cohorts.
- One model for 28 days post Dose 1, one for pre-Dose 2 and one for 28 days post Dose 2
- psVNA responder status enters the model as a categorical variable (coded 1 for responder and 0 for non-responder).
- Other considerations as for the linear regression models

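### Post-dose 1 results are tabulated only by full planned regimen, so arms that share the same first injection are summarised separately and post-dose 1 geometric means lose precision

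*SAP*

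**What the plan says.** **Safety.** SAP 7.6 says "Safety data will be analyzed by study intervention regimens as designed per protocol". The footnote to that sentence, printed under SAP 7.6.3, explains that "the statistical tables are designed with the planned vaccine regimens as columns". Post-dose 1 is one of the display periods within those columns, and the denominator is regimen-specific: "Denominator for the percentages is the number of participants in the considered population and phase for a certain regimen".

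**Immunogenicity.** SAP 7.7.1 says "Data will be analyzed by vaccine regimen, and by vaccine regimen and participant seropositivity status at screening", with results shown at each scheduled time point. For VNA and S-ELISA, SAP 7.7.1.5.1 plans geometric means with 95% CIs, computed on the log10 scale.

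**Pooling.** SAP 7.1.5 says "All analyses are planned to be performed within each cohort separately, unless explicitly indicated that data will be pooled across cohorts". SAP 7.1.2 allows active periods to be combined, but says nothing about combining regimens. Regimens are pooled only in the regression models (7.7.1.7), the COVID-19 harm monitoring (7.7.2) and the infection and vaccine efficacy analyses (7.7.3). No table or graph is planned that groups participants by what they have received so far.

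**Which arms exist.** The footnote under 7.6.3 gives, as an example of a planned regimen, an active 5x10^10 vp dose followed by placebo. SAP 7.7.1.7 lists "Control variables: single-dose vs. two-dose regimen and high-dose vs. low dose regimen". The full regimen list is left to the protocol.

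**The concern.** Before the second injection, a participant assigned to active then placebo and a participant assigned to active then active at the same dose level have had the same treatment. Within a cohort, any difference between their post-dose 1 AEs, or between their titres 28 days after dose 1 or before dose 2, is chance. Showing them as separate columns spreads one estimate over two smaller samples and invites the reader to interpret noise between them.

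The outcomes affected are not peripheral. Solicited and unsolicited AEs after each primary-regimen vaccination are primary endpoints (SAP 7.3), and VNA and ELISA responses are secondary (SAP 7.4.1). The additional split by serostatus, planned for both safety and immunogenicity, thins the columns further.

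**Working it through.** The SAP gives no arm sizes and no precision figure for post-dose 1 data, so there is no stated figure to reproduce. Its only group sizes are the totals in 7.7.3 (860 active, 185 placebo).

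**1. Geometric mean CIs.** The half-width on the log10 scale is t × SD / √n. If two arms of equal size n share the first dose, pooling gives 2n:
- split / pooled width = √(2n) / √n = √2 ≈ 1.41 (ignoring the small change in t);
- reduction on pooling = 1 − 1/√2 ≈ 29%.

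This ratio does not depend on n or SD. With 1:2 allocation, the reduction is 1 − √(1/3) ≈ 42% for the smaller arm and 1 − √(2/3) ≈ 18% for the larger.

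**2. The same on the titre scale.** The CI runs from GMT ÷ f to GMT × f, with f = 10^(t × SD / √n). SD = 0.5 log10 and the arm sizes are assumptions.

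| n per arm | f, one arm | f, pooled (2n) |
|---|---|---|
| 50 | 1.39 | 1.26 |
| 100 | 1.26 | 1.17 |
| 150 | 1.20 | 1.14 |

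**3. AE incidence.** The SAP plans counts and percentages here, so the effect is on the denominator and not on a printed interval. For an assumed 10% rate and 100 per arm, the standard error is √(0.1 × 0.9 / 100) = 3.0 percentage points in one column and √(0.1 × 0.9 / 200) = 2.1 points pooled.

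**4. Rare events.** For an assumed 1% event and 100 per arm:
- the chance that one given column is non-zero is 1 − 0.99^100 = 63.4%;
- the chance that a pooled column is non-zero is 1 − 0.99^200 = 86.6%;
- the chance that at least one of the two separate columns is non-zero is also 1 − 0.99^200 = 86.6%.

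Pooling changes where an event is shown, not whether the trial sees it.

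**5. What the regressions supply.** SAP 7.7.1.7 fits psVNA, wild-type VNA and ELISA at 28 days post-dose 1 and pre-dose 2, plus a Firth logistic model for psVNA responder status. All pool every cohort and every regimen containing active vaccine, with dose level as a term. They therefore yield an adjusted dose-level contrast on pooled data. They do not yield a GMT or responder percentage per first dose within a cohort, and they do not cover safety.

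**The case against.** The strongest reply is that nothing here is wrong. Regimen columns are valid and unbiased, safety is descriptive, and no immunogenicity hypothesis is tested. Fixed columns also let the same participants be followed from baseline past dose 2, and the SAP leaves output detail to the Data Presentation Specifications, which could add a column. All of that stands, and it limits the point to efficiency. It does not remove the point, because the SAP does not commit to a pooled display. AE counts can be added by eye, but geometric mean CIs need reworking, and the medians and quartiles planned for the cellular assays cannot be recombined from the tables.

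Several stronger readings are tempting, and the SAP does not support them:
- **That reactogenicity CIs would narrow.** The statistics listed in 7.6 for safety include no confidence intervals. Nor does 7.7.1.5.1 specify one for responder rates.
- **That rare events are more likely to be missed.** Step 4 of the working shows that the trial's chance of observing one is the same.
- **That the post-dose 1 dose comparison is available only from split columns.** For antibody responses, the 7.7.1.7 models already make it on pooled data.
- **That every cohort is affected.** The matching arms are inferred from an example regimen and two model covariates. Cohort 2a has a one-dose primary regimen and no post-dose 2 period, while Cohort 2b has two doses. If these are analysed as separate cohorts, pooling single- and two-dose primary regimens within cohort does not arise there.

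**Conclusion.** The point holds as a modest loss of precision in descriptive output. Where a cohort contains regimens that share a first dose, the planned tables split one post-dose 1 estimate across columns. With equal arms, geometric mean 95% CIs are about 1.41 times as wide on the log scale as they need be, and AE percentages have half the available denominator. With unequal arms, the loss is larger for the smaller arm and smaller for the larger one.

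This rests on two assumptions that the SAP does not settle: that such matching arms exist within a cohort, and their relative sizes. Both can be read from the protocol. No type I error, sample size or efficacy conclusion is affected. The change is worth making because it costs little and sharpens the post-dose 1 summaries of primary and secondary endpoints.

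**What to change.** In SAP 7.6 and 7.7.1, for the post-dose 1 period and the 28-days-post-dose-1 and pre-dose-2 time points, add columns by first-dose product actually received (placebo, low dose, high dose). Do this within each cohort that has more than one regimen sharing that first dose. Keep the regimen columns alongside, and use regimen columns alone from dose 2 onward.

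The wording should also say whether a participant whose full sequence is not a planned regimen enters the first-dose columns, because the footnotes to 7.6 and 7.7.1 exclude such participants from the tables.

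The cost is a few sentences in the SAP, one grouping variable and some extra table columns. No new data are needed, and neither alpha nor sample size changes.
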